## SUMMARY OF CHANGES

Section	Change
September 18, 2018	
Cover Page	Updated version and date
TOC	Updated TOC
3.1	
 
- Added eligibility criteria of needing a PSA level result within 2 months of assessing eligibility.
 
- Clarified the KPS should be within 3 months of assessing eligibility.
 

11	Updated study calendar to match updates to eligibility
January 23, 2018	
Throughout protocol	Formatting
Cover Page	Updated version and date
Schema	Updated Schema
TOC	Updated TOC
5	Removed any mention of a 2 nd research only scan during the 1 st imaging PSMA imaging visit. The 2 nd research only scan, detailed in Section 11- Correlative studies, is no longer part of the project.
5.1.3	Removed the option to obtain a diagnostic CT with the PSMA scan.
5.5	Updated references to tables and other sections since Correlative studies section was removed.
5.6	Continuing with surgery is at the discretion of the referring physician after reviewing the PSMA imaging results.
5.7.1	Added the option to repeat PSMA imaging.
5.10	Removed “Extraordinary medical circumstances”, not appropriate for this study.
6.1	Changed baseline data collection window from 30 day to 3 months prior to PSMA imaging.
6.2	Clarified pre-imaging assessments.
6.3	Clarified post-imaging assessments.
6.4	Added laboratory section
11	Removed Correlative studies section. The research only scan will not be obtained.
11	Study Calendar updated to reflect changes in the protocol.
12	Updated all references to tables and other sections since Correlative studies section was removed.
13	Updated all references to sections since Correlative studies section was removed.
November 28, 2017	
Cover Page	Updated version and date, and added a biostatistician
12	Added optional 2 nd PSMA PET/CT scan if medically indicated
November 21, 2017	
Cover Page	Corrected IND # 135,727, updated version and date
7.1	Corrected  Ga PSMA-HBED-CC IND # 135,727

**October 31, 2017**

---

[figure not shown]
Cover Page	Added IRB #, IND #, and updated dated version and date
Schema	Updated Schema
TOC	Updated TOC
1.1.1	Specifie regional “pelvic” nodal metastases
5.4.5	Changed from central blind reader to internal blind readers. Also clarified reference to central blind reader to internal blind readers through remainder of study protocol.
5.5	Referenced Section 13 rather than having same information in multiple places in the protocol.
6	Clarified Patient Assessment section, added potencial research CT if clinical follow-up imaging is not obtained.
7.1	Added  Ga PSMA-HBED-CC IND # 135,272
12	Clarified footnotes in study calendar
13	Updated Efficacy Assessment – This is the same information that was in the previous section 13, however, laid out in a way to more easily evaluate the PSMA scam, conventional imaging and pathology assessment.
14.1	Statistical Justification section added
14.2	Updated section references throughout, as information in Section 13 was moved around.
14.3	Updated section references throughout, as information in Section 13 was moved around.

**April 20, 2017**

---

Receipt	v0.06
	Initial submission to FDA, 1571 0000

## 1. OBJECTIVES

### 1.1. Primary objective

- 1.1.1. Determine sensitivity, specificity, positive, and negative predictive value of  $^{68}\text{Ga}$  PSMA-HBED-CC PET for detection of regional pelvic nodal metastases compared to pathology at radical prostatectomy (per patient, using nodal regional correlation).

### 1.2. Secondary objective

- 1.2.1. Determine sensitivity, specificity, positive, and negative predictive value of  $^{68}\text{Ga}$  PSMA-HBED-CC PET for detection of extra-pelvic nodal metastases, visceral metastases, and osseous metastases compared to biopsy and imaging follow-up.

### 1.3. Exploratory objectives

- 1.3.1. Determine sensitivity, specificity, positive, and negative predictive value for detection of regional nodal metastases in comparison to cross-sectional imaging performed contemporaneously with  $^{68}\text{Ga}$  PSMA-HBED-CC PET.
- 1.3.2. Compare progression free survival at one year (as measured by PSA) between patients with, and without, nodal metastases.
- 1.3.3. Correlate SUVmax from  $^{68}\text{Ga}$  PSMA-HBED-CC PET and short-axis diameter (of nodal disease on cross-sectional imaging) to presence of true pathology.
- 1.3.4. Quantify and describe the incidence of osseous and distant metastatic lesions.

## 2. BACKGROUND AND RATIONALE

### 2.1. Current imaging of prostate cancer

Prostate cancer is the most commonly diagnosed cancer and second leading cause of cancer death in American men. Existing conventional imaging (CT, MRI and bone scans) has a low sensitivity in detecting local recurrence or metastatic disease. The one exception is NaF PET/CT for the detection of osseous metastasis. Due to this limitation, numerous approaches to stage patients have been evaluated.

C-11 and F-18 Choline PET imaging have been frequently used, as prostate cancer exhibits increased choline uptake that has been associated with increased cell membrane proliferation and increased levels of choline kinase. Choline uptake is increased in comparison to FDG in both androgen dependent and independent prostate cancer patients. Choline has also been shown to be sensitive for the detection of recurrent tumor, although sensitivity is somewhat lower in patients with PSA (prostate specific antigen) values of less than 1.0 ng/ml. There are two forms of choline that are used in imaging prostate cancer, C-11 and F-18 choline. C-11 choline has a short half-life of 20 minutes, which limits its detection for metastatic disease but results in improved local detection due to decreased urinary activity at the time of imaging. F-18 choline has significant urinary excretion that limits evaluation of the prostate but, has been shown to have better detection rates for distant metastatic disease. C-11 choline has limited sensitivity for osseous metastasis, possibly due to

the decreased uptake time. Additionally, the sensitivity of C-11 choline is limited in patients with PSA values < 1.0 ng/ml. Although choline PET may be limited in sensitivity, it clearly shows more lesions than cross section imaging or bone scan in patients with known disease. In 2012, the Mayo Clinic obtained a new drug application approval from the FDA for the use of C-11 choline.

A separate approach is to image prostate specific membrane antigen (PSMA). PSMA is expressed on the majority of prostate cancer cells, and so is an ideal target to image. The initial imaging approach to target PSMA was done using Indium-111-capromab (Prostascint), a murine monoclonal antibody. Although there was early promise for the detection of nodal metastasis, the agent does not adequately visualize osseous metastasis and has limited sensitivity, although combination with SPECT/CT does improve lesion detection. One main limitation to In-111-capromab is that it takes a prolonged time to localize to the target tissue, which relates to both the size of the monoclonal antibody and its slow pharmacokinetics. Additionally, Prostascint also recognizes an intracellular epitope, so the antibody must cross the membrane to be effective. This likely only occurs in permeable dead or dying tumor cells.

Because of the limitations of In-111 capromab, there have been continued efforts to develop agents that target the extracellular domain of the PSMA protein. The Ga-68 labeled PSMA-HBED-CC compound has become of particular interest due to two important publications. The first study demonstrated that PSMA-HBED-CC has a higher sensitivity for the detection of disease than F-18 choline in a head-to-head intra-patient comparison that included 37 patients. The second paper looked at the sensitivity of PSMA-HBED-CC in detecting metastatic lesions in patients with recurrent prostate cancer. Their results demonstrated a detection rate of 50% for patients with a PSA less than 1 ng/ml, and detection rate above 85% for patients with a PSA greater than 2 ng/ml. These detection rates are significantly higher than that reported by groups using choline.

## 2.2. **Ga PSMA-HBED-CC (Ga PSMA-11)**

Current evidence regarding detection rate of biochemical recurrence (BCR) with Ga-HBED-CC PSMA PET/CT from two recent papers:

- Detection rate was 50% when PSA was below 0.5 ng/mL, 69% for PSA 0.5–2.0 ng/mL, and 86% when PSA was above 2.0.
- Detection rate was 57.9% for PSA 0.2 to <0.5 ng/mL, 72.7% for PSA 0.5 to <1, 93.0% for 1 to <2.0, and 96.8% for  $\geq$  2.0.

## 2.3. **Prior human subjects experience**

**Safety.** No adverse drug reactions have been reported in the literature for Ga PSMA-HBED-CC. As a PET tracer, the drug should remain pharmacologically inert and not perturb the biological system. Afshar-Oromieh and colleagues as well as Green *et al.* have clearly stated that no adverse events or pharmacologic events were observed during their studies. Adverse events were not discussed in other reviewed studies or case reports. In total, these papers provide data regarding more than 1200 subjects without any noted adverse reactions.

**Efficacy.** To date, there have been 11 studies describing use of Ga PSMA-HBED-CC and 4 clinical trials. Tables with key information of reviewed papers are provided (Tables 6-1, 6-2, and 6-3) in the body of the IND application.

Maurer et al. (2014) [Germany]. The purpose of this retrospective study was to investigate the diagnostic efficacy of Ga PSMA-HBED-CC -PET imaging when compared against radical prostatectomy, templated lymph node dissection, and conventional imaging (CT, MRI). The primary inclusion criterion was intermediate-to-high risk prostate cancer scheduled to undergo radical prostatectomy. The only exclusion criterion was presence, or history, of a secondary malignancy. A total of 130 patients were reviewed. A contrast enhanced diagnostic CT was performed at the same imaging session as the PET scan. A double-trained board certified radiologist-nuclear medicine physician blinded to post-operative histopathological results analyzed all the imaging data sets (Ga PSMA-PET/CT and PET/MR). Conventional imaging was read prior to the Ga PSMA-PET data. Results yielded a patient-based ROC AUC of 0.835 (95% CI 0.763 – 0.908) for Ga PSMA-PET and an AUC of 0.691 (95% CI 0.592-0.789) for conventional imaging. For Ga PSMA-PET patient-based sensitivity was 65.9 %, specificity was 98.9%, and overall accuracy of 88.5%. In contrast, conventional imaging had a patient-based sensitivity of 43.9%, specificity of 85.4%, and an overall accuracy of 72.3%. On a template-based analysis driven by lymph node dissection, the Ga PSMA-PET sensitivity was calculated as 78.2%, specificity as 99.1%, and accuracy as 95.7%. Conventional imaging resulted in a sensitivity of 29.1%, specificity of 97.2%, and accuracy of 86.1%.

Van Leeuwen et al. (2014) [Australia]. The purpose of this prospective trial was to assess accuracy of Ga PSMA-HBED-CC -PET/CT for lymph node staging in intermediate- and high-risk prostate cancer. Criteria for selection included planned radical prostatectomy, treatment naïve, negative bone scan, no concurrent (or history of) a secondary malignancy, and at >5% risk of metastatic lymph nodes. Patients with suspected extra-nodal disease on prior contrast-enhanced CT were excluded. Ga PSMA-HBED-CC PET/CT was performed <4 weeks before the radical prostatectomy and lymph node dissection. A total of 30 men were enrolled and evaluated. A non-contrast enhanced CT was performed at the same imaging session of the Ga PSMA-HBED-CC -PET. Images were analyzed by two nuclear medicine physicians; it is not stated if the physicians were blinded to the pathologic results or if the scan interpretations were completed prior to surgery. Results yielded a patient-based specificity of 95%, sensitivity of 64%, positive predictive value of 88%, and negative predictive value of 82%. Lymph node analysis yielded specificity of 100%, sensitivity of 58%, PPV of 94% and NPV of 98%. The mean size of true-positive metastatic lymph nodes was 4.7 mm ( $\pm$  1.4mm) and false-negative size was 2.7mm ( $\pm$  1.3mm).

Eiber et al. (2015) [Germany]. The purpose of this retrospective study was to investigate the detection rate of Ga PSMA-HBED-CC PET/CT in men with

biochemical recurrence (PSA  $\geq$  0.2 ng/mL). Only men who had undergone a radical prostatectomy, had not received chemotherapy, and had a diagnostic CT done with the PSMA imaging study were included. Men undergoing antiandrogen therapy (n=70) were included. A total of 248 subjects were included in the analysis. The active comparator was the diagnostic CT done simultaneously with the PET imaging. Scans were interpreted by a board certified radiologist and a board certified nuclear medicine physician. The reviewers were not blinded. No significant detection effect was observed with antiandrogen use ( $p=0.0783$ ). PSMA was able to identify additional areas of disease involvement in 61 subjects (24.6%) whereas CT showed additional regions in 17 subjects (6.9%). A significant limitation of the study was a lack of histopathology for outcome comparisons. Sensitivity, specificity, positive and negative predictive values are not provided.

Afshar-Oromieh et al. (2015) [Germany]. The purpose of this retrospective study was to analyze the diagnostic value of  $^{68}\text{Ga}$  PSMA-HBED-CC PET/CT in a large cohort with multiple variables. The cohort was designed to align with a generalized population; men were included if they had suspected progressive disease following conventional therapy (radiation therapy and/or radical prostatectomy, n=292) or to determine metastatic disease burden prior to initial therapy (n=27). Of those with suspected recurrence, 86 were on antiandrogen therapy. A non-contrast enhanced diagnostic CT scan was performed at the same imaging session as the PET scan; additionally, a low-dose attenuation scan was performed for the  $^{68}\text{Ga}$  PSMA-HBED-CC PET. Scans were interpreted by two board-certified nuclear medicine physicians. No adverse events or clinically detectable pharmacological effects were noted in any of the subjects following injection of the PSMA-HBED-CC radiotracer. A total of 901 tumor lesions were observed in 319 subjects. Lesion-based analysis yielded sensitivity of 76.6%, specificity of 100%, negative predictive value of 91.4%, and positive predictive value of 100%. Because all patients were assumed to have tumor and therefore could not be considered 'true negative,' the authors did not provide a per-patient calculation.

Green et al. (2017) [Indiana University School of Medicine, Indiana, US]. The purpose of this small study was to estimate human radiation dosimetry for  $^{68}\text{Ga}$  PSMA-HBED-CC under approval of an RDRC research protocol. Both biodistribution and pharmacokinetics were evaluated in subjects (n = 9). Administered dose of  $^{68}\text{Ga}$  PSMA-HBED-CC was 3.04 mCi and images were acquired at 15 minutes post-injection, 60 minutes post-injection, and 90 minutes post-injection. Subjects reported no symptoms or adverse reactions following radiopharmaceutical administration. Organ dose estimates were provided for 22 organs and for whole body.

It should be noted that radiolabeled PSMA ligands have been shown to be taken up by rectal carcinoma, gastrointestinal stromal tumors, renal cell carcinoma, pancreatic serous cystadenoma, stromal hyperplasia of the breast, B-cell follicular non-Hodgkin's lymphoma, and Paget disease.

**Summary.** To date, a prospective, well-controlled clinical trial evaluating the efficacy of Ga PSMA-HBED-CC PET/CT has not been performed for prostate cancer. Robust trials for both initial diagnosis as well as those men with suspected recurrence needs to be designed and performed. Current retrospective review of Ga PSMA-HBED-CC PET/CT done in foreign nations suggests strong efficacy of the Ga PSMA-HBED-CC radiotracer. Currently, three clinical trials are underway – two foreign, one domestic. Additional pivotal phase 3 trials should be completed in the U.S. to determine effectiveness in the generalized population and determine requirements for implementation if found to be effective.

#### 2.4. **Rationale**

Imaging and staging of prostate cancer is critical for surgical and treatment planning. We aim to image patients with suspected metastatic prostate cancer using Gallium-68 labeled HBED-CC PSMA (Ga PSMA-HBED-CC) in order to determine its utility. We plan to utilize this data to obtain further approvals of the Ga PSMA-HBED-CC compound, so that this agent will become widely available for clinical imaging in prostate cancer patients.

Ga PSMA-HBED-CC has been shown to be superior to choline based Carbon-11 and Fluorine-18 PET imaging agents for the staging of prostate cancer. However, Ga PSMA-HBED-CC was not patented and therefore no company or private entity will make the investment required to bring it to market. In the vacuum of availability, academic groups are taking the lead in order to collect the necessary data for future FDA approval.

The rate of prostatectomy is increasing in high-risk prostate cancer patients (1), which means that there is an increasing unmet need to detect regional and distant metastases prior to surgery. Two published studies to date using Ga PSMA-HBED-CC PET in intermediate to high-risk patients prior to prostatectomy, demonstrated a per patient sensitivity for nodal metastases of 64-66% (2,3), much improved compared to conventional imaging modalities. We aim to study the ability of Ga PSMA-HBED-CC to detect pelvic nodal disease in intermediate and high-risk preprostatectomy patients.

### 3. SUBJECT SELECTION

#### 3.1. Eligibility Criteria

- 3.1.1. Biopsy-proven prostate adenocarcinoma
- 3.1.2. Intermediate to high-risk disease, defined as one of the following factors: PSA > 10, T2b or greater, or a Gleason score of 7 or greater.
- 3.1.3. A PSA level result within the last 2 months.
- 3.1.4. Planned prostatectomy with lymph node dissection
- 3.1.5. Karnofsky performance status (KPS) of  $\geq 50$  (ECOG/WHO 0, 1, or 2) within the last 3 months.
- 3.1.6. Must be treatment naïve (not have received neoadjuvant chemotherapy, radiation therapy, hormonal therapy, androgen deprivation therapy, or focal ablation techniques (e.g., HiFu)
- 3.1.7. Not receiving any other investigational agents (i.e., unlabeled drugs or drugs under an IND for initial efficacy investigations
- 3.1.8. Ability to understand and the willingness to provide informed consent.

#### 3.2. Exclusion Criteria

- 3.2.1. Cannot receive furosemide.
- 3.2.2. Allergy to sulfa or sulfa-containing medications.
- 3.2.3. History of Stevens-Johnson syndrome
- 3.2.4. Known Paget's disease
- 3.2.5. Uncontrolled intercurrent illness including, but not limited to, ongoing or active infection, symptomatic congestive heart failure, unstable angina pectoris, cardiac arrhythmia, or psychiatric illness/social situations that would limit compliance with study requirements.

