## 12.2. Reference standard definition:

12.2.1. Histopathology/Biopsy will be the primary determinate of tissue positivity and negativity for prostate cancer disease. Pathology date, organ, and location as well as any notes related to the pathology will be obtained from the subject chart. The anatomical region/sub-region the pathology occurred in will be assigned by the investigator team:

Ga-PSMA-HBED-CC positive findings are aimed to be confirmed by histopathology/biopsy if clinically feasible. Pathology performed 60 days before or after the Ga-PSMA-HBED-CC PET will be available for correlation.

Histopathological procedures and biopsies will be performed as clinically indicated and as per institutional protocol.

12.2.1.1. Lymph Nodes, Visceral Lesions, and Bone Lesions positive for disease by pathology.

- Lesions with positive pathologic confirmation will be regarded as positive for disease. The regionality of the resected tissue will be assigned into respective regions and sub-regions as described above in Table 12.2.

12.2.1.2. Lymph Nodes and Visceral Lesions negative for disease by pathology.

- Tissue removed and negative for pathology are considered negative for prostate cancer disease, unless subsequent conventional imaging or Ga-PSMA-HBED-CC PET imaging demonstrates that targeted tissue were not resected. In this case:

- i. Subjects can be rescanned with dedicated CT, MRI, or Ga-PSMA-HBED-CC PET/CT to determine if the suspicious Ga-PSMA-HBED-CC tissue was removed. If the tissue is confirmed as removed, this is considered negative for disease.

ii. If  $^{68}\text{Ga}$ -PSMA-HBED-CC PET/CT positive tissue is still present, a needle biopsy can be pursued at the discretion of the treating physician. Images of the procedure will be reviewed to determine if the correct tissue was biopsied.

- If the  $^{68}\text{Ga}$ -PSMA-HBED-CC PET/CT positive tissue was biopsied, a negative pathologic finding of the biopsied tissue is considered negative for disease.
- If the  $^{68}\text{Ga}$ -PSMA-HBED-CC PET/CT positive tissue was biopsied, a positive pathologic finding of the biopsied tissue is considered positive for disease.
- If biopsy or re-biopsy is not performed, or the wrong tissue was biopsied, change in node size as measured by conventional imaging and as defined below will be the criteria by which disease status will be defined.

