12.2.1.3. Bone lesions: Given the high rate of false negative biopsies for osseous metastases in subjects with prostate cancer, subjects with negative bone biopsies of  $^{68}\text{Ga}$ -PSMA-HBED-CC PET positive lesions will be further evaluated:

- If pathology demonstrates an alternative diagnoses that is known to be  $^{68}\text{Ga}$ -PSMA-HBED-CC positive (eg Renal Cell Carcinoma metastases, Paget's disease), then this will be considered negative for disease.
- If pathology is indeterminate, then follow-up imaging as described below will be performed as per clinical standards at the site.

12.2.1.4. Although not routinely performed during standard practice, immunohistochemical staining for PSMA of tumor specimens (primary and lymph node metastases) may be performed, although not required.

12.2.1.5. All regions not sampled for biopsy/histopathology will be designated as indeterminate for disease by pathology. Conventional imaging follow-up may be used in these cases to determine tissue status.

12.2.2. Follow-up Imaging will be used as a secondary assessment for prostate cancer in the event pathology information is not available:

All subjects will be tracked for follow-up conventional imaging between 3-12 months post  $^{68}\text{Ga}$ -PSMA-HBED-CC (dedicated CT, MRI and/or bone scan) as per site standard of care. If no follow-up imaging has been performed within the 9 months following the  $^{68}\text{Ga}$ -PSMA-HBED-CC scan, then the research study will pay for an additional follow-up CT scan to be performed in the 9-12

month window post-Ga-PSMA-HBED-CC scan. Follow up imaging will only be performed on subjects that have positive Ga-PSMA-HBED-CC findings because conventional imaging assessment for disease is primarily targeting suspicious lesions identified by Ga-PSMA-HBED-CC PET/CT. Interpretation of follow-up imaging will be performed by local read. Preferably, the follow-up conventional imaging should be the same modality/modalities as the initial staging work-up to allow for reproducible and accurate comparisons. Conventional imaging standards as described below will be used to determine tissue positive for prostate cancer disease. Conventional imaging will not be used to determine negative prostate cancer disease regions due to its inherently low negative predictive value.

Tissue positive for prostate cancer disease based on follow-up imaging:

12.2.2.1. Lymph nodes will be assessed by change in size.

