  - If PSA increases by more than 25% (PCWG3 definition of recurrence) on systemic therapy, then an increase in the size of lesion by more than 20% in the long axis diameter will be considered positive for disease.
- b. In subjects with localized suspected lesions(s) receiving targeted treatment without concomitant systemic treatment there are two ways to meet positive disease criteria:
  - If the subject demonstrates a decrease of PSA by greater than 50% after targeted treatment [OR]
  - If on post-treatment follow-up imaging within 3-12 months, lesions seen on CT or MRI decrease by more than 30% in long axis diameter (with a minimum of 3 mm in change in size)
- c. For untreated subjects: If on follow-up imaging within 3-12 months, lesions seen on CT or MRI increase by more than 20%

in long axis diameter (with a minimum of 3 mm in change in size).

ii. Negative for disease:

- Conventional Imaging follow up will not be used for assessment of negativity for disease

iii. Indeterminate for disease

- Regions with no visceral lesions determined to be positive by the conventional imaging criteria described above and without pathology will be designated as visceral regions indeterminate for prostate cancer disease.
- Prostate bed and prostate regions not determined to be positive by the conventional imaging criteria described above and without pathology will be designated as prostate regions indeterminate for prostate cancer disease.
- Subjects that have had neither pathology sampling, nor conventional imaging follow up will have all prostate and visceral regions designated as indeterminate for disease by reference standard.

12.2.2.3. Bone lesions will be considered:

i. Positive for disease on baseline assessment:

- Any positive sclerotic lesion on the CT portion of the Ga-PSMA-HBED-CC PET or on a separate CT obtained  $\leq$  30 days before or after the PET/CT.
- Focal uptake on the baseline bone scan performed within one month of Ga-PSMA-HBED-CC PET.
- Any MRI lesion in bone read as positive on the initial MRI performed within one month of Ga-PSMA-HBED-CC PET.

ii. Positive for disease on follow up:

- Any new positive sclerotic lesion on CT within 12 months of Ga-PSMA-HBED-CC PET scan
- Any new MRI bone lesion within 12 months of Ga-PSMA-HBED-CC PET scan
- Any new focal uptake in bone within 12 months of Ga-PSMA-HBED-CC PET scan

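### An unbiopsied node or visceral lesion from a known second cancer can be scored as prostate cancer on size change alone

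*Combined protocol and SAP*

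**What the plan says.** **Known sources of non-prostate uptake.** Section 2.3 warns that "radiolabeled PSMA ligands have been shown to be taken up by rectal carcinoma" and goes on to six further conditions. Of the seven, four are malignant: rectal carcinoma, gastrointestinal stromal tumour, renal cell carcinoma and follicular lymphoma. Paget disease, pancreatic serous cystadenoma and breast stromal hyperplasia are not cancers.

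**Eligibility.** Of those seven, Section 3.2 names only "Known Paget's disease". The nearest general criterion is 3.2.5, "Uncontrolled intercurrent illness including, but not limited to, ongoing or active infection". No criterion in 3.1 or 3.2 mentions a second malignancy, present or past. Both pre-prostatectomy studies described in 2.3 barred it. For the retrospective one, "The only exclusion criterion was presence, or history, of a secondary malignancy"; for the prospective one, the selection criteria included "no concurrent (or history of) a secondary malignancy".

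**Reference standard.** Pathology comes first (12.2.1): "Histopathology/Biopsy will be the primary determinate of tissue positivity and negativity for prostate cancer disease". Imaging is the fallback (12.2.2): "Follow-up Imaging will be used as a secondary assessment for prostate cancer in the event pathology information is not available". For a visceral lesion the untreated rule begins "For untreated subjects: If on follow-up imaging within 3-12 months, lesions seen on CT or MRI increase by more than 20" per cent, measured on the long axis with a 3 mm minimum. The nodal rule in 12.2.2.1 is the same on the short axis. Imaging follow-up can return positive or indeterminate, never negative.

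**The concern.** A man with, say, a known renal or bowel cancer may have a PET-positive node or visceral deposit from that cancer. If it is not sampled and it grows, the written rule makes it prostate cancer, and 13.3.1 then counts the scan as a true positive. A finding that should count against the tracer, or not count at all, is credited to it.

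No later step catches this. The blinded readers see no other clinical data (12.1). The follow-up readers are told where the PET-positive lesions are and measure them (6.4.2), but no rule tells them to discount another known tumour. The baseline data in 6.1 do not include cancer history, so a later sensitivity analysis is not assured either.

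The results are meant to support further approvals (2.4) and to set the target sensitivities for a larger study (13.1). An upward error would carry into both.

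**Working it through.** The plan gives no figure on this point, and the half-widths in 13.1 neither support it nor depend on it. The check is first a reading of the rules side by side, then a small illustration.

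**Where size change alone is enough, with no tissue**

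| Lesion and setting | What makes it reference-positive | Size alone enough? |
|---|---|---|
| Node or visceral, untreated | Growth over 20%, at least 3 mm | Yes |
| Node or visceral, targeted treatment only | Shrinkage over 30%, at least 3 mm; or a route based on PSA decline | Yes, by the first route |
| Node or visceral, systemic treatment | Size change together with a PSA change | No |
| Bone | Sclerosis, MRI lesion or focal uptake; PSA decline after targeted treatment | Size not used |

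The only rule that sets aside another PSMA-avid diagnosis by name is 12.2.1.3. It covers bone, and only when pathology shows the alternative. For nodes and visceral lesions, protection comes from negative tissue (12.2.1.2), and biopsy is at the treating physician's discretion (5.7.3).

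**Route to each endpoint**

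- Secondary: 13.3.1.1 and 13.3.1.2 accept imaging positivity under 12.2.2.1 and 12.2.2.2 directly.
- Primary: 13.2.1.2 and 13.2.1.3 lead back to 12.2.1.2 and 12.2.2.1. The node must be PET-positive, left behind at surgery, not correctly biopsied, and then meet the size rule.

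**Illustration, secondary endpoints (all counts assumed).** Take one lesion per region: three PET-positive lesions, two of them prostate cancer and one an unsampled second primary that meets the size rule, plus one true prostate lesion missed by PET. Sensitivity is taken as TP/(TP+FN); the different denominator printed in 13.1 is a separate matter.

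- As written: TP = 3, FN = 1. Sensitivity = 3/4 = 75%. PPV = 3/3 = 100%.
- After the fix, lesion non-evaluable (13.3.5.1): TP = 2, FN = 1. Sensitivity = 2/3 = 67%. PPV = 2/2 = 100%.
- After the fix, if the indeterminate lesion were instead scored by a literal reading of 13.3.3 (imaging shows it is not positive): FP = 1. Sensitivity = 2/3 = 67%. PPV = 2/3 = 67%.

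**Range.** Let k be the number of true prostate lesions, with one missed and one second primary. Sensitivity is k/(k+1) as written and (k−1)/k after the fix:

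| k | As written | After the fix |
|---|---|---|
| 2 | 2/3 = 66.7% | 1/2 = 50.0% |
| 3 | 3/4 = 75.0% | 2/3 = 66.7% |
| 5 | 5/6 = 83.3% | 4/5 = 80.0% |

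If PET misses no true lesion, sensitivity is 100% either way.

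**Illustration, primary endpoint.** The rounded rates of the cited 30-man prospective study (sensitivity 64%, specificity 95%, PPV 88%, NPV 82%) fit TP 7, FP 1, TN 18, FN 4: 7/11 = 63.6%, 18/19 = 94.7%, 7/8 = 87.5%, 18/22 = 81.8%. Suppose, in a table of that size, that the one false-positive man instead had an unresected second-primary node meeting the size rule. As written, sensitivity is 8/12 = 66.7%; with him non-evaluable it is 7/11 = 63.6%. The difference is about 3 points.

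**The case against.** The strongest reply is that the case is rare and partly guarded against. Every man is planned for prostatectomy with node dissection (3.1.4), the surgeon is told where PET-positive pelvic nodes lie and should try to capture them (5.6.2), and resected tissue without prostate cancer is negative. PET-positive findings are meant to be confirmed by tissue where feasible (12.2.1). Criterion 3.2.5 is open-ended and could be read to cover an active, uncontrolled cancer. Criterion 3.1.6, read broadly, could keep out men given chemotherapy or radiation for another cancer. This is also a 30-man descriptive pilot with no significance testing.

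Most of this stands as a limit on frequency. It does not close the gap: a past or controlled cancer, or one treated by surgery or only observed, passes both criteria, and nothing in 12.2.2 then asks about it.

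Several stronger readings are tempting, and the documents do not support them:

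- *PPV is inflated from 67% to 100% and a fix restores it.* Once the lesion is non-evaluable, PPV in the example is 2/2, still 100%. It is 2/3 only under the literal reading of 13.3.3. The larger reason PPV sits high is that imaging can never return a negative, which is a different issue.
- *Any size change counts, at any site.* Systemic treatment also requires a PSA change. That is partial protection, since 12.2.2 does not fix the PSA baseline. Bone rules do not use size.
- *Paget's disease was excluded because of false uptake.* Sections 2.3 and 12.2.1.3 make this plausible, but 3.2 gives no reason.
- *Second malignancy must be an exclusion because the cited studies made it one.* Their choices do not bind this design, and 2.3 looks toward effectiveness in a general population.

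**Conclusion.** The gap is real and narrow. The reference standard can certify a known other tumour as prostate cancer when the lesion is a node or visceral deposit, no tissue settles it, and the man is untreated or has had targeted treatment only. For a PET-positive lesion the error can only favour the tracer.

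Its main reach is the secondary extra-pelvic nodal and visceral endpoints. A reader might infer that the primary endpoint is generally compromised. It is not: that endpoint rests mainly on surgical pathology and is exposed only through a pelvic node neither resected nor correctly biopsied. The osseous endpoint is outside the mechanism.

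The size rests on assumed counts. The documents give no rate of second malignancy, and there may be no such man among 30. If there is one, with one true lesion missed, sensitivity is overstated by about 3 points (five true lesions) to 17 points (two true lesions), and by 8 points in the main example. The change is worth making because the error follows from the rule as written, runs in one direction for PET-positive lesions, and is cheap to remove.

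**What to change.** Add one sentence to 12.2.2: in a man with a known current or past second malignancy of a type that could explain the lesion, a node or visceral lesion is reference-positive only with prostate cancer histology; otherwise it is indeterminate and is classed as non-evaluable under 13.3.5.1 (13.2.5.1 for pelvic nodes). Naming the non-evaluable class matters, because a literal reading of 13.3.3 would otherwise turn the same lesion into a false positive.

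Add cancer history, with type, to the baseline data in 6.1 so that the rule can be applied.

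The cost is a few more indeterminate lesions and one baseline item. No new exclusion criterion and no additional biopsy is required. Excluding every man with a past cancer would also close the gap, but it would narrow the population and is not needed.
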